7.2.4 Safety variables

Incidence of all adverse events and complications by severity and relationship to study device.

Treatment tolerability as measured by a questionnaire.

7.3 Study Hypothesis

H_0 : The proportion (%) of subjects reporting freedom from pain at 2 hours post treatment without rescue medications in the treated group = The proportion (%) of subjects reporting freedom from pain at 2 hours post treatment without rescue medications in the sham group.

H_A : The proportion (%) of subjects reporting freedom from pain at 2 hours post treatment without rescue medications in the treated group \neq The proportion (%) of subjects reporting freedom from pain at 2 hours post treatment without rescue medications in the sham group.

7.4 Sample Size Estimation

The sample size for this study was calculated to test the above described null hypothesis with a chi-squared test, even though the final analysis may employ a regression model.

In the pilot study, the percentage of responders in the relevant treatment arm was 30%, while the percentage of responders in the sham group was 6%. The latter result is consistent with sham response rates referenced in IHS Guidelines for Migraine Trials. Sample size calculations are based on a more conservative estimate of the sham group response rate of 10%, then a sample size to detect a difference between treated and sham groups (of 20%) with 80% power at a 5% level of significance will result in a total of 124 evaluable subjects, with 62 subjects randomized to the treated arm and 62 to the sham arm. Allowing for a ~10% drop-out rate, a total of 136 (68 treated vs. 68 sham) subjects may be enrolled in the study.

Statistical considerations require availability of 124 evaluable subjects, i.e. with data available for analyses. The study recruitment will be monitored closely via the EDC system and, as soon as the evaluable data target is achieved, the Study Monitor will receive notification. If the number of subjects enrolled in the US is at least 50% of the accumulated population, recruitment will be stopped.

7.5 Interim Analysis

According to [24-26], planning an interim analysis that permits an increase in the sample size as described below does not inflate the type I error. In addition, the final analysis is performed using the conventional test as appropriate for the statistical hypothesis.

One interim analysis is planned once 50% of the information is collected, i.e. the interim look will be performed after 62 evaluable subjects have been accrued. After all the relevant data will be

entered into the database, a soft lock to the database will be performed. An unblinded statistician will perform the assessments described below. A designated Data Monitoring Committee will recommend whether to stop the study once the interim results are available.

The study will then either continue to the originally planned sample size if the result is “favorable”, stop for futility if the result is “unfavorable”, or an increase will be made to the sample size if the result is “promising”. These decisions will be made based on the conditional power (CP), defined as the conditional probability that the result will exceed a critical value at the interim given the observed effect size $\widehat{\delta}_1$ = difference between response rates treated versus control at the interim look.

Notation:

n_1 = sample size at interim analysis

n_2 = sample size calculated based of effect size obtained at interim

n_{max} = the highest sample size the company is willing to use/ can afford, $n_{max} = 248$ subjects and is calculated based on a smaller effect size of 15% in the same manner as above.

CP_{min} =is the calculated minimum CP based on the ratios n_{max}/n_2 , n_1/n_2 and the target study power (80%).

The following are the decision rules for the interim analysis which will be performed upon accrual of 50% (n_1/n_2) of the sample size, i.e. 62 evaluable subjects. These depend on the zone into which CP falls at the interim, the calculated CP_{min} , the maximum sample size designated for the study and the % of the originally planned sample size at which the interim analysis will be performed. Following this principle does not inflate the Type I error.

1. If the result is “Unfavorable”, i.e. $CP < CP_{min} = 36\%$ (interim result is so disappointing that it is not worth increasing the sample size to retrieve conditional power), continue to the original sample size of 124. If the difference between response rates at the interim ($P_t - P_c$) is less than 0 (i.e. control is better than treatment) stop the trial for futility.
2. If the result is “Promising”, i.e. $36\% \leq CP < 80\%$, the sample size is increased to recover the targeted power of 80%. The sample size used will be either the new calculated sample size based on the conditional power (as described in Sample size re calculation using conditional power Jonathan S. Denne Statist. Med. 2001; 20:2645–2660) or the predetermined maximum sample size of 248 subjects whichever lower.
3. If the result is “Favorable”, i.e. $CP \geq 80\%$ the interim results are sufficiently favorable and trial continues to the original sample size planned of 124 without the need to adaptively increase the sample size.

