Back-up of the database is performed daily. In addition, copy of each participant's ePROs and other activity is stored in his/her smartphone memory and can be retrieved in case such need occurs.

Study database will be locked and exported using EDC tools into SAS compatible format for interim and final statistical analyses.

Query resolution will be performed using EDC tools.

All paper based source data and relevant medical documents meant to serve also as source documents will be maintained by the sites and available as eCRF attachments. Patient identification will be blackened from all data. Patients will be identified by their codes. The site investigator is responsible for ensuring that eCRFs are filled in a timely manner and relevant paper documents are properly stored. Investigator will provide the documents to the sponsor either through the sponsor representative or by mail per sponsor request.

Access to data will be authorized and controlled, in accordance with relevant laws and guidelines.

Study will be performed according to the protocol. At each site, the PI will appoint staff member(s) that will be responsible for completing the Case Report Forms supplied by the sponsor.

Specifics of data query handling are given in Data Management and Monitoring plans.

Audit trail for data entry and corrections will be maintained.

6.4.5 *Procedures for Review of Data*

A detailed description of data queries, their resolution and overall data flow can be found in the Data Management Plan.

Missing PRO data will be identified by a dedicated software running on the cloud closely to real time. Corresponding queries will be issued to study participants and site study coordinator. Effort will be made to resolve such queries as close as possible to real time.

6.4.6 *Data Monitoring Committee*

An independent Data Monitoring Committee (DMC) is charged with the task of providing regular oversight of the data monitoring issues as detailed in the document: "DMC". These experts will periodically review and evaluate the accumulated data for study progress. The DMC will make recommendations concerning continuation, modification, or termination of the study. The Data reviewed by the DMC will include a summary of the following topics:

- Study progress: Subject recruitment, comparison with targeted recruitment, retention, protocol adherence, and quality of data collection procedures.
- Treatment Monitoring: Data on treatment integrity and adherence.

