- Safety Monitoring: Data related to the safety of the subjects, including any adverse events or side effects related to the treatment.
- Efficacy monitoring: Interim efficacy analysis is to be performed per algorithm presented in Section 7.5.
- Futility monitoring: Futility will be assessed at the time of interim analysis.

6.4.7 *Total Expected Duration of the Clinical Investigation*

The anticipated duration of the study is up to 18 months.

6.5 *Subjects*

6.5.1 *Inclusion Criteria*

Patients need to fulfill all the below Inclusion criteria:

1. Patient is 18-75 years old.
2. Patient meeting the ICHD-3 diagnostic criteria for migraine with and without aura
3. Patient reporting 2-8 migraine attacks per month.
4. Patient must be able and willing to comply with the protocol
5. Patient must be able and willing to provide written informed consent
6. Male or non-pregnant / non-lactating female (NOTE: Females of child bearing potential must have a negative pregnancy test and must be willing to use adequate contraceptive means during the study)
7. Possesses the basic cognitive and motor skills needed to operate android cell phone

6.5.2 *Exclusion Criteria*

Patients are excluded if they have any of the following:

1. Has other significant pain problem that in the opinion of the investigator may confound the study assessments
2. Is currently implanted with an electrical and/or neurostimulator device (e.g. cardiac pacemaker or defibrillator, vagus nerve neurostimulator, deep brain stimulator, spinal stimulator, bone growth stimulator, cochlear implant, Sphenopalatine ganglion stimulator or Occipital nerve stimulator).
3. Known uncontrolled epilepsy.
4. Use of Cannabis including medical use.
5. Has chronic migraine (more than 15 headache days per month).
6. Changed usage or dosage of migraine preventive medications in the last two months
7. Has undergone nerve block (occipital or other) in the head or neck within the last 2 weeks.
8. Is participating in any other clinical study.

6.5.3 *Contraindications*

Contraindications for the use of the Nerivio Migra device include those known for transcutaneous electrical stimulation procedures. In addition to restrictions described in exclusion criteria, Nerivio Migra shall not be placed over open wounds or burns, or on irritated skin.

The Nerivio Migra is **NOT** intended for use in any other location except the upper arm.

6.5.4 *Number of Subjects*

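### Section 7.5 prescribes opposite actions for an 'unfavorable' interim result: the summary sentence stops for futility, while decision rule 1 continues to 124

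*Combined protocol and SAP*

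**What the plan says.** Section 7.4 sets the target: 30% vs 10% responders, "with 80% power at a 5% level of significance will result in a total of 124 evaluable subjects". Section 7.5 plans one look at 62 evaluable subjects, with conditional power (CP) deciding among three zones.

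The section describes the action for the lowest zone twice.

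- **Summary sentence.** The study will "stop for futility if the result is “unfavorable”, or an increase will be made to the sample size" if the result is promising. The next sentence bases these decisions on CP.
- **Rule 1 of the numbered list.** 'Unfavorable' means CP below 36%. The result is then so poor that "it is not worth increasing the sample size to retrieve conditional power), continue to the original sample size of 124". A separate condition follows: if the treated-minus-sham difference "is less than 0 (i.e. control is better than treatment) stop the trial for futility".

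The list is introduced with "The following are the decision rules for the interim analysis". On authority to stop, the section says: "A designated Data Monitoring Committee will recommend whether to stop the study once the interim results are available".

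Section 6.4.6 (Data Monitoring Committee) gives the committee the task of "providing regular oversight of the data monitoring issues as detailed in the document" named there. It adds: "Interim efficacy analysis is to be performed per algorithm presented in Section 7.5". On futility it says only that it will be assessed at the interim. Section 16.1 allows termination on a DMC futility recommendation but gives no criterion.

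**The concern.** Both texts use the same label, and both tie it to CP. They agree only when sham is ahead, where both stop. For every result with CP below 36% and treatment level with or ahead of sham, one text stops the trial and the other continues it to 124.

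The unblinded statistician and the DMC act on this section. If the ambiguity is noticed only after the look, whoever resolves it already knows which reading helps, and the rule is no longer prespecified. At stake are the power promised in Section 7.4 and the clarity of the instruction to the DMC.

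**Working it through.** **Inputs.** From Section 7.4: 30% vs 10% responders, 62 per arm, 80% power, 5% level; also the pilot rates of 30% vs 6%. From Section 7.8.1: two-sided tests. From Section 7.5: interim at 62 (31 per arm), CP limits 36% and 80%, cap 248.

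**1. Reproduce the planned size.** Per arm n = [1.96·√(2·0.2·0.8) + 0.8416·√(0.3·0.7 + 0.1·0.9)]² / 0.2² = (1.1087 + 0.4610)² / 0.04 = 61.6. This rounds up to 62 per arm, or 124 in total, as stated. The 36% limit also reproduces: the promising-zone calculation with interim fraction 0.5, maximum twice the planned size and 80% target gives 35.8%.

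**2. CP under the observed trend.** With z₁ the interim pooled z statistic and the look at half of 124, CP = Φ(2z₁ − 1.96·√2) = Φ(2z₁ − 2.772). CP = 36% at z₁ = 1.207, CP = 80% at z₁ = 1.807, and a tie (z₁ = 0) gives CP of about 0.3%. The conflict zone is therefore 0 ≤ z₁ < 1.207. For pooled response rates of 10% to 20% (an assumed range), that is an observed difference from 0 up to about 9 to 12 percentage points.

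**3. Example with 3/31 sham responders.**

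| Treated | z₁ | CP | Summary sentence | Rule 1 |
|---|---|---|---|---|
| 2/31 | −0.47 | <0.1% | stop | stop |
| 3/31 | 0 | 0.3% | stop | continue to 124 |
| 6/31 | 1.08 | 27% | stop | continue to 124 |
| 7/31 | 1.38 | 50% | increase | increase |

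The texts conflict for 3 to 6 treated responders.

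**4. How often, and at what cost.** I enumerated all binomial outcomes exactly. In the promising zone the total was raised in steps of 2 until CP reached 80%, capped at 248. The final test is the two-sided 5% chi-squared test, and only a result favouring treatment counts as success.

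| True rates | Treated behind sham | Opposite actions | Success, rule 1 | Success, summary sentence as binding stop |
|---|---|---|---|---|
| 30% vs 10% | 1.3% | 18.2% | 84.6% | 76.0% |
| 30% vs 6% | 0.2% | 7.6% | 96.6% | 91.2% |
| 10% vs 10% | 41.5% | 47.7% | 2.45% | 1.73% |

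At 30% vs 10%, CP is below 36% in 1.3% + 18.2%, or about 19.6% before rounding. Of the conflicting trials, (84.6 − 76.0)/18.2, or about 47%, would reach significance if continued.

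**5. Sensitivity at 30% vs 10%.** Without the promising-zone increase, power is 80.9% under rule 1 and 72.3% under the binding stop. By normal theory with the increase, it is 82.7% vs 73.1% with pooled variance and 84.9% vs 75.5% with unpooled variance.

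**6. Type I error.** Over common response rates from 2% to 50%, the largest one-sided rate is 0.0264 under rule 1 and 0.0188 under the binding stop. The fixed 124-subject chi-squared design with no interim has 0.0294.

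**The case against.** The strongest reply is that the summary sentence is only a loose preview. It sets no thresholds and cannot be applied without the numbered list. That list is announced as the decision rules, and its definition of 'unfavorable' sits beside its action. On that reading Section 7.5 already has one algorithm, with a futility stop when sham is ahead.

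Much of this stands. Rule 1 is the more natural operative text. But no text supplied states which governs, and the summary sentence cannot be confined to results with sham ahead, because it uses the same labels and is tied to CP.

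Three stronger readings are tempting, and the documents do not support them.

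- A reader might infer that the trial as planned is underpowered. The loss needs the less likely text to govern, the stop to be automatic, and rates near 30% vs 10%. Section 7.5 has the DMC recommend, and Section 16.1 says the study may be discontinued. An advisory stop would cost less, and at the pilot rates power stays about 91% even with a binding stop.
- A reader might infer inflated type I error. Neither reading exceeds the fixed design's maximum.
- A reader might infer that the rule is unresolved everywhere. Section 6.4.6 names a DMC document, and Sections 6.2, 7.8 and 9 refer to a separate SAP. Neither was available for this review, and either may settle the point.

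**Conclusion.** The contradiction is real and lies in the current text of one section. It covers a region that is not rare: 18.2% of trials at the design rates and 47.7% under no effect. It should be removed before the unblinded look.

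The statistical consequence is conditional. Under rule 1, the stated 80% power is kept or exceeded. Under a binding stop on every 'unfavorable' result, power at 30% vs 10% is about 76% by exact calculation, 73% to 75.5% by normal theory depending on the variance used, and about 72% without the sample-size increase.

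These figures assume 31 evaluable subjects per arm at the look, CP under the observed trend, and standard CP-based re-estimation. The last is an assumption because Section 7.5 cites its re-estimation formula without printing it. The conflict itself does not depend on that formula.

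**What to change.** Reconcile the two texts before the unblinded interim so that Section 7.5 states one action for 'unfavorable'.

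- **If rule 1 is intended**, reword the summary sentence: favorable or unfavorable, continue to 124; promising, increase up to 248; stop for futility only if the treated-minus-sham difference is below 0.
- **If a stop whenever CP is below 36% is intended**, change rule 1 to say so and restate power at 30% vs 10% as about 76%, giving the method.

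In either case, check that the DMC document and any separate SAP say the same, and state whether the stop is binding or advisory.

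The first option costs one sentence and the document check. Sample size, cap, CP limits and final analysis do not change. The second also changes the power statement. Either change goes through Section 9: IRB/EC approval, or notification if it counts as non-substantial. The waiver in Section 7.8 refers to the statistical analyses section and does not clearly extend to Section 7.5.

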7.6 Randomization

After a subject meets the eligibility criteria, he/she will be randomly allocated (with a 1:1 ratio) to one of the following 2 treatment groups based on a randomization scheme using the permuted block method stratified by preventive medications use and center:

- Sham Control
- Nerivio Migra group

The randomization scheme will be prepared by the study statistician using the SAS (version 9.4.) random number procedure. The block size will be fixed and study personnel will be blinded to the randomization block size.

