3.9 Summary of Necessary Training

General instructions and training in device use as per the IFU will be provided to study participants at the participating sites. No specific skills are required from study participants beyond basic level of experience with general purpose Android applications. Training will be delivered by designated study personnel and will be recorded in a corresponding CRF. In addition,

records of the training session will be recorded in the study DB with label “training”. The criteria for training effectiveness will be ability of the participant to run a training treatment session independently. At the end of the session, the device will be switched into operational mode by “sliding off” training mode indicator on the main screen of the application.

Training to the investigator and staff will be delivered by Theranica representative in a frontal session including demo and training activations. In order to provide additional support to clinical personnel, a training clip was recorded and will be available at all training sessions for staff and participants.

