6 DESIGN OF THIS CLINICAL STUDY

6.1 *Description*

This is a prospective, randomized, double-blind, sham controlled multi-center clinical trial “Migraine Treatment with Nerivio Migra electro stimulation device”. The study will enroll up to 248 patients diagnosed with migraine with and without aura, per the inclusion and exclusion criteria. These patients will be individually and randomly assigned to either treatment group or control group. For sham control, short electrical pulses of amplitude range similar to that of the treatment programs will be administered at very low frequency (0.1-0.5 Hz). The rationale underlying selection of sham control settings is that, on the one hand, pulses are perceivable and the user is able to manipulate their intensity similarly to the case of treatment programs, while, on the other hand, no clinically relevant treatment is delivered, based on existing knowledge of parameters range of electro stimulation treatments [5-7, 18].

Following successful screening, enrollment interview and signing of informed consent, participants will be provided with an active Nerivio Migra or identically looking sham device and trained to perform treatment and provide feedback via the smartphone application. Ratio between treatment and control groups will be 1:1.

Baseline information including mean frequency and severity of migraine attacks, occurrence of other headaches, presence of ICHD-3 diagnostic criteria for migraine with and without aura and use of preventive and rescue medications will be recorded.

Investigational devices will be programmed in active or sham mode with a 1:1 ratio, in order to achieve the desired ratio between active and control groups sizes, stratified with by use of preventive medications.

Study flow is schematically presented in the figure below.

[figure not shown]

Figure 4. Study Design

Following enrollment, the study will be conducted in three stages.

Stage One. In stage one (roll-in phase) recruited participants will be reporting their migraine attacks per ICHD-3 diagnostic criteria, including presence of aura, using an electronic migraine diary installed on their smartphones. Duration of this phase is one month.

Stage Two. This will be the parallel arm treatment stage.

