6.2.2 Procedures to ensure blinding

This is a double-blind study: neither the patient, nor the investigators will be aware of arm allocation of each study participant. Maintaining double blind design is a known challenge in non-invasive neuromodulation devices trials. A number of means are planned to ensure the double blind aspect of this trial.

Selection of identically looking, active sham devices as control means is only a single step aimed at maintaining blindness. Each device will be numbered with 3 digit numbers, first digit site number and two digit subject numbers. Each new patient will be provided with d next consecutive numbered device.

Adherence to randomization procedure by clinical staff is critically important.

Importance of adherence to study design and procedures will be explained to participants in the course of enrollment.

No information regarding expected stimulation perception will be provided, except for the fact that stimulation intensity adjustment control will allow to adjust intensity to "a well perceived but non-painful" level.

In order to achieve blinding, participants will be trained individually. A training clip will be used for training, in order to minimize staff exposure to participants' reaction to and tolerability of treatment intensity.

In the course of the trial, participants will not be asked directly any questions regarding treatment perception.

The clinical staff will be instructed to not engage in any discussions regarding anticipated treatment perception.

End of study questionnaire will include individual blinding assessment to examine whether the blinding was well maintained throughout the study.

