APPENDIX A. STIMULATION PROGRAMS

- Waveform: Biphasic, rectangular, symmetrical
- Duration of primary phase (μsec): 200
- Pulse duration (μsec): 400
- Pulse frequency (Hz): 100-120*
- Max output current (mA): 60

* In order to avoid habituation (i.e., cease of response to the stimulus), Migra employs frequency drifting in the following manner – after each 5-minute section of the treatment, the frequency of the output will toggle between 100-110-120Hz.

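### A fixed block size leaves avoidable allocation certainty if staff can infer past arms; undisclosed random block sizes of at least 4 would remove most of it at little cost (minor improvement)

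*Combined protocol and SAP*

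**What the plan says.** **Randomization.** Section 7.6 has subjects "randomly allocated (with a 1:1 ratio") by a "permuted block method stratified by preventive medications use and center". It then adds: "The block size will be fixed and study personnel will be blinded to the randomization block size". The size itself is not given.

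**Dispensing.** Section 6.2.2 states: "Each new patient will be provided with d next consecutive numbered device". On numbering it says: "Each device will be numbered with 3 digit numbers, first digit site number and two digit subject numbers".

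**Stimulation.** Section 6.1 says sham pulses "will be administered at very low frequency (0.1-0.5 Hz"). Appendix A gives the active program as "Pulse frequency (Hz): 100-120". Section 6.1 also says that sham pulses can be felt and that the user can adjust their intensity.

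**Training.** Section 3.9 has designated study personnel deliver the training and states: "The criteria for training effectiveness will be ability of the participant to run a training treatment session independently". Section 6.6.2 puts randomization, device hand-out and training in the same visit.

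**Safeguards.** Section 6.2.2 acknowledges that double blinding is hard in this kind of device trial. It lists identical-looking devices, individual training with a video clip intended to minimize what staff see of reactions, no description of the expected sensation, no staff discussion of it, and a blinding assessment at the end of the study.

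**The concern.** Permuted blocks force the last allocations in each block. Someone who knows the earlier arms in a stratum and the block length knows those last allocations before the next patient is enrolled. A constant length can in principle be worked out from a run of known arms, so withholding it protects only while past arms stay hidden.

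Here there is a possible route to past arms. The participant runs a session at the site on stimulation of very different frequency in the two arms, and the next device is always the next number. Some eligibility decisions rest on judgment (Section 6.5.1, ability and willingness to comply; Section 6.5.2, confounding pain in the investigator's opinion), and Section 6.5.6 counts a patient as enrolled only after training. Foreknowledge of the next arm could therefore influence who is enrolled. At stake is the comparability of the two groups, which randomization is there to protect.

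**Working it through.** **Inputs from the documents**
- 1:1 allocation; fixed, unstated block size; strata of center by preventive medication use (Section 7.6).
- Sham 0.1–0.5 Hz (Section 6.1); active 100–120 Hz (Appendix A).
- 30% vs 10% responders, 80% power, 5% level, 124 evaluable (Section 7.4); two-sided tests (Section 7.8.1).

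**Assumptions, because the documents give no figure**
- Fixed block sizes of 4, 6 or 8.
- 24 patients in a stratum.
- Staff infer past arms with 100% or 80% accuracy.

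**1. The plan's own sample size.** n per arm = [1.96·√(2·0.2·0.8) + 0.8416·√(0.3·0.7 + 0.1·0.9)]² / 0.2² = (1.109 + 0.461)² / 0.04 = 61.6, so 62 per arm and 124 in total. This reproduces Section 7.4. Power at 62/62 is 80.3%. The documents give no figure for predictability.

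**2. Frequency contrast.** The smallest ratio is 100 / 0.5 = 200.

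**3. Certain allocations, fixed block of size m, past arms and m known.** The expected share forced is 2/(m + 2):
- m = 4: 2/6 = 33.3%
- m = 6: 2/8 = 25.0%
- m = 8: 2/10 = 20.0%

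**4. Overall correct guesses, same conditions.** P = 0.5 + (2^m / C(m, m/2) − 1) / (2m):
- m = 4: 0.5 + (16/6 − 1)/8 = 70.8%
- m = 6: 0.5 + (64/20 − 1)/12 = 68.3%
- m = 8: 0.5 + (256/70 − 1)/16 = 66.6%

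**5. Is concealing the size enough?** By simulation, a guesser who knows past arms but not the block size, and simply picks the arm with fewer patients so far, is right 70.8% / 68.4% / 66.6% of the time for blocks of 4 / 6 / 8. If that guesser also ignores the medication stratum (40% use assumed), the figures are about 64% / 62% / 60%. Concealment therefore does not stop guessing once past arms are known.

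**6. Random block sizes.** Simulation, with past arms and the set of sizes known:

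| Design | Certain | Correct overall |
|---|---|---|
| Fixed 4 | 33.3% | 70.8% |
| Fixed 6 | 25.0% | 68.3% |
| Fixed 8 | 20.0% | 66.6% |
| Random 2, 4 | 10.1% | 72.0% |
| Random 2, 4, 6 | about 4% | about 70% |
| Random 4, 6 | 5.6% | 68.7% |
| Random 4, 6, 8 | about 2.5% | about 67% |

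Certainty falls sharply; overall guessing hardly moves. Sets that include blocks of 2 are guessed more often than fixed 6 or 8, and the 2, 4 set more often than fixed 4.

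**7. Imperfect inference.** With past arms inferred at 80% accuracy, correct guesses are 60.1% / 58.0% / 56.8% for fixed 4 / 6 / 8 and 56.7% for random 4, 6, 8. Nothing is certain in either design.

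**8. Cost.** With random 4, 6, 8, a stratum list cut off at 24 patients has a mean imbalance of about 0.5 to 0.6 patients and a maximum of 4. Power at a total of 124 is 80.5% with 58 active and 66 sham, and 79.7% with 66 active and 58 sham, against 80.3% at 62/62.

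**The case against.** The strongest answer is that the plan already conceals the block size and takes specific steps against unmasking at training, and that an undisclosed fixed block is a coherent choice. No section says that the arms feel different or that staff can tell them apart. Each participant has one device, so nobody compares the two sensations, and staff would have to infer the arm from a reaction that the video clip is meant to keep from them. Consecutive dispensing also stops staff choosing a device. If unmasking does happen at training, that is the real defect, and block size does not cure it.

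Most of this stands, and it sets the limits of the point. A reader might infer that site staff will be able to predict allocations. The documents do not support that: prediction depends on inferring past arms, and that ability is nowhere shown. A reader might also infer that varying the block size removes predictability. The calculation shows otherwise: overall guessing stays near 67%, and at 80% accuracy the designs differ little.

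What the objection does not dispose of is that the clip reduces exposure without ruling it out, and that concealing the size gives little protection once past arms are known. For that case, the fixed size adds certainty that the design does not need.

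**Conclusion.** A minor, optional improvement; Section 7.6 contains no error on this point. If staff could infer past arms and work out the fixed size, about 20% to 33% of allocations would be certain in advance (blocks of 8 to 4). Undisclosed random sizes of 4, 6 and 8 would bring this to about 2.5%. These figures are upper bounds: they assume perfect knowledge of past arms, of the patient's stratum and of the block size or set of sizes. With imperfect inference there is no certainty to remove, and the gain is at most a few percentage points of guessing accuracy. The size of any resulting bias in the primary comparison cannot be estimated from the documents.

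A related matter needs reconciling. Section 6.2.2 describes one consecutive device series per site, with no digit for the medication stratum, whereas Section 7.6 stratifies by that factor within center, and Sections 6.1 and 6.2.1 name only preventive medication as a stratifier. How the stratified lists map to device numbers should be stated.

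**What to change.** In Section 7.6, replace the sentence that fixes the block size with: *Block sizes will vary at random within each stratum (for example 4, 6 and 8; no blocks of 2); the sizes and sequence are known only to the statistician who prepares the scheme and are not disclosed to study personnel.*

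This takes one sentence and a small change to the SAS randomization program, for lists not yet in use. The downside is a slightly larger possible imbalance where a stratum's list ends part-way through a block. Blocks of 2 are left out because they raise overall guessing.

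This does not deal with possible unmasking at training. If the sponsor wants to address that directly, training could be given by staff who take no part in screening or enrollment, at the cost of extra personnel at each site.
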